### **5.5.1 Adverse events**

A table showing the number and percentage of events as well as the number and percentage of patients with at least one event will be provided for any AE and for AE according to SOC and PT.

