4.5 Safety Evaluation

Safety will be evaluated by collection of AEs and SAEs from entry into the study through the 12 months follow-up visit, or until the subject has terminated participation in the study. All adverse events will be followed until they are adequately resolved or stabilized or for 1 month following study completion or termination, whichever comes first.

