4.7.3 Pharmacological Treatment

As recommended by the GOLD guidelines, each subject will continue maintenance bronchodilator therapy, which will include an inhaled long-acting beta agonist, inhaled anticholinergic, or both. These drugs may also be combined with theophylline and/or inhaled corticosteroids at the discretion of the treating physician. The physician will be allowed to adjust the subject's pharmacological regimen as needed during the course of the study to deal with variations in the subject's condition (e.g., COPD exacerbations). However, the subject's medical regimen should be optimized at the pre-Treatment Visit, prior to completing the baseline Six Minute Walk Test and pulmonary function tests. Medically necessary changes in medications or dosages will be recorded in the CRF. Supplemental oxygen utilization should be recorded and monitored throughout the Study.

All subjects enrolled in the study must have current influenza and pneumococcus vaccinations consistent with local recommendations and/or policy.

Prophylactic anti-inflammatory treatment with steroids 50mg/day shall be given 1 day prior, during and after each treatment for up to 15 days. Prophylactic treatment with antibiotics can be considered for at least 5 days if some bleeding occurs during the implantation and there are infiltrations on chest x-ray post Tx or patient has an excess secretion or sputum culture shows pathologic concentration. Pseudomonades effective antibiotics are needed only in case of positive culture in sputum.

Table 3. Visit Schedule

Procedure / Assessment	Visit 1 Baseline Screening (at least 7 days prior to Tx1)	Tx1 RePneu Placement	Visit 2 1 month post Tx1	Tx2 RePneu Placement (4-8 weeks post Tx1)	Visit 3 1 month post Tx2	Optional Tx3 RePneu Placement (4-8 weeks post Tx2)	Visit 3 4 months post final Tx	Visit 4 12 months post Tx1
Informed Consent	X							
Inclusion/ Exclusion	X							
Focused physical exam including vital Signs and SpO ₂	X	X	X	X	X	X	X	X
Spirometry	X						X	X
Lung volumes	X						X	X
6MWT	X						X	X
SGRQ	X						X	X
mMRC	X						X	X
Concomitant medication / O ₂ Use	X	X	X	X	X	X	X	X
Pregnancy testing	X	X		X		X		
Physical activity and energy expenditure for 6-8 days	X						X	X
Bronchoscopic still images			X		X		X	
Static and dynamic pulmonary compliance prior and post Tx			X		X		X	
Echocardiogram	X						X	X
Body composition	X						X	X
V/P SPECT or Lung perfusion scintigraphy	X							X
High Resolution CT	X							X
Chest X-Ray	X	X		X		X		

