7.5 Process for Assessment, Recording and Reporting of AEs

Subjects will be instructed at the beginning of the study to report to the investigator any adverse physical or mental changes they experience and they will be asked about adverse events at each visit, including those experienced at the baseline visit prior to, during, or immediately following treatment, as assigned. All such adverse events reported by the subjects or observed by the investigators will be reported to the Sponsor.

As described in Section 7.0, if the event is deemed to be Serious, such events will be reported to the Sponsor via the completion of the Adverse Event CRF. The Ethics Committee(s) will be informed if the Serious or unexpected adverse event, in the opinion of the Investigator, or the Medical

Monitor, is likely to affect the safety of the subjects or the conduct of the study.

8 Administrative

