### **5.5.2 Serious adverse events**

A table showing the number and percentage of events as well as the number and percentage of patients with at least one event will be provided for any serious AE and for serious AE according to SOC and PT.

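### The all-cause AE and SAE tables have no onset cut at the first procedure and use an eligibility-defined set, so their percentages do not measure risk after coil treatment

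*SAP*

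**What the plan says.** **Collection.** Protocol 4.5 states: "Safety will be evaluated by collection of AEs and SAEs from entry into the study through the 12 months follow-up visit". Protocol 7.5 adds that subjects are asked about events at every visit, "including those experienced at the baseline visit prior to, during, or immediately following treatment". The visit schedule (Protocol Table 3) marks adverse events at Visit 1 and places that visit "at least 7 days prior to Tx1", with no upper limit.

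**Tabulation.** SAP 5.5.1 (Table 14.6.1) specifies that the "number and percentage of patients with at least one event will be provided for any AE and for AE according to SOC and PT". SAP 5.5.2 (Table 14.6.2) gives the same counts, "provided for any serious AE and for serious AE according to SOC and PT". Neither section limits events by onset date. SAP 5.5.3 (Table 14.6.3) selects events by relation to device or procedure, again without an onset limit.

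**Analysis set.** SAP Appendix I assigns all three tables to ITT. SAP 3.1 defines ITT as subjects who meet the inclusion and exclusion criteria; having had a procedure is not part of the definition.

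**Timing information.** The AE listing in SAP 5.5 carries the AE start date, the procedure dates and the days since procedures. SAP 3.4.3 fills in a missing day as the first of the month and a missing month as January. If the resulting date falls before the first procedure, it is replaced by the day after discharge from that procedure.

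**The concern.** This is a single-arm study of an implanted device, so readers will take the AE and SAE percentages as the risk that follows coil placement. Protocol Table 2 presents earlier coil data in that way: SAEs per procedure up to 6 months, set beside a sham group. The largest row there is COPD exacerbation or pneumonia, and an exacerbation between baseline and Tx1 would be counted under the same terms.

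As the SAP stands, two things other than post-coil events enter Tables 14.6.1 and 14.6.2: events before any coil was placed, which go into the numerator, and eligible patients who never had a procedure, who go into the denominator. No table separates either. The study stopped early with fewer patients than planned, so a single patient can visibly move a percentage.

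**Working it through.** The plan states no event rate that depends on this point, so there is no figure of its own to reproduce. The check is of the text, followed by an illustration of size.

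**Text.** Four statements are enough:
- The collection window opens at study entry (Protocol 4.5).
- Entry precedes Tx1 by at least 7 days (Protocol Table 3).
- The tables take any AE and any serious AE (SAP 5.5.1, 5.5.2).
- The set is defined by eligibility (SAP 3.1).

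The SAP's only date rule that refers to the first procedure (3.4.3) re-dates events and removes none. Pre-treatment events are therefore counted.

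**Which patients change the percentage.** A pre-treatment event changes the proportion with at least one event only if the patient has no event afterwards. With a constant rate r per year, a window of t years before Tx1 and 12 months of follow-up:

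increase = [1 − exp(−r·t)] × exp(−r)

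*Illustration A: assumed rates.* The documents give neither r nor t. Taking r = 1, 2, 4 events per year and 2, 4, 8 weeks (t = weeks/52.18), the increase in percentage points is:

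| r per year | 2 weeks | 4 weeks | 8 weeks |
|---|---|---|---|
| 1 | 1.4 | 2.7 | 5.2 |
| 2 | 1.0 | 1.9 | 3.6 |
| 4 | 0.3 | 0.5 | 0.8 |

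For the middle cell: 1 − exp(−2 × 4/52.18) = 14.2%; exp(−2) = 13.5%; 14.2% × 13.5% = 1.9 points.

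*Illustration B: a rate from the documents.* The sham-control column of Protocol Table 2 gives 18/107 = 16.8% over 6 months for COPD exacerbation or infection (SAEs only). Treating this as the probability of at least one event in 182.5 days:

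λ = −ln(1 − 18/107)/182.5 = 0.00101 per day

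Counted from Tx1 over 365 days, incidence is 1 − exp(−365λ) = 30.8%. Counted from entry, w days earlier, it is 1 − exp(−(365 + w)λ). The pre-treatment share of event counts is w/(w + 365).

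| w (days) | Incidence from entry | Increase (points) | Share of event counts |
|---|---|---|---|
| 7 | 31.3% | 0.5 | 1.9% |
| 30 | 32.9% | 2.1 | 7.6% |
| 60 | 34.9% | 4.1 | 14.1% |

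Only the 7-day minimum comes from the protocol; 30 and 60 days are assumptions.

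**The opposite effect.** Suppose one ITT patient in ten is never treated and is observed only for the 30-day window (both assumptions). That patient's incidence is 1 − exp(−30λ) = 3.0%. The table would show 0.9 × 32.9% + 0.1 × 3.0% = 29.9%, which is below the 30.8% counted from Tx1. The net error can go either way.

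**Partial dates.** Suppose Tx1 falls on the 20th and an event is recorded with only the month before. SAP 3.4.3 sets it to the first of that month, finds this earlier than Tx1, and moves it to the day after discharge. An event known to precede treatment then appears as post-treatment in the listing, and it would pass a simple onset cut.

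**The case against.** The strongest reply has four parts.

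- **The tables match the protocol.** Protocol 4.5 evaluates safety from study entry, and the SAP tabulates that window. This is right: the documents do not contradict each other here. The point is that the resulting percentage answers a different question from the one readers will ask.
- **Attribution handles it.** Table 14.6.3 is limited to device- and procedure-related events, and an event before Tx1 should not be judged related to a procedure not yet performed. This stands for Table 14.6.3, which needs no change. It does not help the all-cause tables.
- **The listing shows timing.** In a small, stopped study a line listing is a workable display, and the accountability table shows how many patients had a first procedure. This stands in part. The reader would have to rebuild the tables by hand, and the partial-date rule can hide the events in question.
- **The effect is small.** This largely stands, as the illustrations show.

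A reader might go further and infer that the coil's own event rates are inflated by 10 to 20 percentage points. At 2 events per year and 4 weeks, 14.2% of patients have a pre-treatment event, or 1 to 2 of an assumed 10. The documents do not support that inference. Most of those patients would have a later event and be counted anyway, so the increase is 1.9 points, about 0.2 patients in 10. Tables 14.6.1 and 14.6.2 are also all-cause tables for the study, not coil-attributed rates.

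**Conclusion.** The point holds for Tables 14.6.1 and 14.6.2. As specified, their percentages combine pre-treatment events, and possibly never-treated patients, with post-coil events, and so do not measure risk after treatment.

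The effect is probably modest. Pre-treatment events alone add about 0.3 to 5 points to patient-level incidence in Illustration A, and about 0.5, 2 and 4 points at 7, 30 and 60 days in Illustration B. For windows of 7 to 60 days they make up about 2% to 14% of event counts. These figures assume a constant rate and a full 12 months of follow-up. Shorter follow-up would raise the patient-level figures, and a higher event rate after the procedure would lower them. Illustration B covers one category of serious event, observed after a sham bronchoscopy, so it is a rough anchor only.

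Upward bias cannot be claimed overall, because untreated patients in the denominator work against it. The case for the change rests on a clear definition at almost no cost, not on a large expected error.

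**What to change.** In SAP 5.5 and 3.4.3:

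1. Define a treatment-emergent event as one with onset on or after the start of the first bronchoscopy.
2. Base Tables 14.6.1 and 14.6.2 on treatment-emergent events, with patients in whom at least one procedure was started as the denominator. Leave the attribution rule for Table 14.6.3 as it is.
3. Show events from study entry to Tx1 as a separate block of the AE listing, so that the full collection window in Protocol 4.5 is still reported.
4. Restrict the partial-date rule so that an event known to have started before Tx1, for example from its recorded month or because it was reported at Visit 1, is not re-dated to after it. Where the known part of the date leaves the order open, the present rule can stay.

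The cost is one definition, one programmed flag, one restriction on an imputation rule and a little extra output. The AE start dates and procedure dates are already planned for the listing, so no new data are needed.

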### **5.5.2 Serious adverse events**

A table showing the number and percentage of events as well as the number and percentage of patients with at least one event will be provided for any serious AE and for serious AE according to SOC and PT.

### **5.5.3 Device and Procedure Related Adverse Events**

A table showing the number and percentage of events as well as the number and percentage of patients with at least one event will be provided for any device and procedure related AE and for device and procedure related AE according to SOC and PT.

### **5.5.4 Deaths**

A listing for deaths will be provided for the final analysis, consisting of the following information:

- Subject ID
- Date of death
- SOC

- PT
- Time slot
- Related to emphysema
- Related to device
- Related to procedure
- Timing of death

If no deaths occur, the output will be produced either way. In this case a programmers note will be shown, stating that no deaths occurred throughout the study.

### **5.5.5 Device Removal**

A listing for all removed devices will be created if any devices have been removed at the time of the analysis.

## **5.6 Effectiveness analyses**

The following summary listing of effectiveness parameters will be produced for the final analyses showing the following parameters at baseline, at assessed visits, change from baseline to assessed visits and, for some variables, if the MID was reached for (Responder):

- 6MWT in m over time (Responder:  $\geq 25m$ )
- Forced expiratory volume in one second (FEV1) (Responder:  $\geq 10\%$ )
- Residual volume (RV)
- Residual volume/total lung capacity (RV/TLC)
- Diffusion capacity (DLCO)
- mMRC dyspnea scale
- Heart rate
- Body composition including BMI

### **5.6.1 Primary effectiveness endpoint**

Changes at 3 months post final treatment and 12 months post first treatment in:

- Minute Walk Distance (6MWD)

The change from baseline as continuous variable and the responder analysis as categorical variable will be presented.

### **5.6.2 Secondary effectiveness endpoints**

Due to the small sample size, the secondary effectiveness endpoints will only be listed. The assessments and change from baseline will be presented per patient in the efficacy listing.

## APPENDIX I: OVERVIEW OF TABLES, FIGURES AND LISTINGS TO BE PRODUCED

### Overview of planned tables

Programmer Note: Please adapt the numbering of subgroup tables as may be necessary.

Table Number	Title	Analysis Set for Final Analyses	Subgroup Analyses 
14.1.1	Patient accountability	ITT	No
14.1.2	Study terminations	ITT	No
14.2.1	Enrollment by site	ITT	No
14.2.2	Demographics	ITT	No
14.2.3	Baseline characteristics	ITT	No
14.2.4	Medical history	ITT	No
14.2.5	History and characterization of emphysema	ITT	No
14.2.6	Treatment of emphysema	ITT	No
14.3.1	Number of devices implanted	ITT	No
14.3.2	Procedure time	ITT	No
14.3.3	Post-procedure hospital stay	ITT	No
14.6.1	Adverse events	ITT	No
14.6.2	Serious adverse events	ITT	No
14.6.3	Device and procedure related adverse events	ITT	No
14.7.1	Change from baseline in 6MWT in m	ITT	No
14.7.2	Number and percentage of patients achieving change in 6MWT in m $\geq 25$	ITT	No

### Overview of planned figures (on request)

Figure Number	Title	Analysis Set For Final Analyses
1	Patient accountability	ITT

### Overview of planned listings

Listing Number	Title	Analysis Set For Final Analyses
16.1	Study Patients	ITT
16.2	Protocol Deviation	ITT
16.3	Baseline Data	ITT
16.4	Procedural Data	ITT
16.4	Overview of safety variables	ITT
16.5	Overview of deaths	ITT
16.6	Overview of effectiveness variables	ITT
